#### 8.6.3 DSMB Plan

The DSMB, will be chaired by [name] a Professor of Psychiatry at Columbia University College of Physicians and Surgeons and a senior expert in mood disorder pharmacotherapy. Three additional faculty members from the division will join the DSMB;

- [name] Ph.D, a senior researcher in the division, with more than 30 years of experience in the early phases of medication development for substance use disorders;
- [name], an opioid dependence treatment investigator in the division, and
- [name], another research psychiatrist in the division.

Finally, [name], Site Chief of the Division of Plastic Surgery and a Professor of Surgery at Columbia University Medical Center, will be on the DSMB and will provide surgical expertise.

The DSMB will meet before the study launch and quarterly afterwards to conduct initial and ongoing study review and review all AEs that occurred in the study. The DSMB will meet within a week of the occurrence of any SAE. For each SAE, the PI and covering physician will present a synopsis of how it occurred and how the incident was handled clinically so that DSMB can assess how the event was managed and if there are any recommendations that will maintain the high quality of the care that we provide to our research participants. Ad hoc meetings may also occur as needed to address study related issues.

All DSMB members will be asked to submit in writing any potential conflict of interest pertaining to the study. The DSMB will prepare a report in response to any SAE review meetings and will submit a DSM report annually. Reports will be submitted to the Sponsor and other authorities as appropriate. This report will include the following:

a) Brief description of the trial,

b) Baseline socio-demographic characteristics,

c) Retention and disposition of study participants,

d) Quality assurance issues,

e) Regulatory issues,

f) AEs,

g) SAEs

h) Efficacy.

## 9 CLINICAL MONITORING

This study may be participant to audit or inspection by representatives from the NYSPI IRB, DSMB or FDA.

Data from this study will be monitored by staff from the CRO, Clinilabs, for compliance with GCP principals. Monitoring will include review of CRFs and other study documents for protocol compliance, data accuracy and completeness. Monitoring will include review of the investigator's site file and drug handling records. Clinilabs will be given direct access to source documents, CRFs and other study-related documents. By signing the informed consent form, the participant authorizes Clinilabs staff direct access to their medical records and the study data.

### **10 STATISTICAL CONSIDERATIONS**

#### **10.1 STATISTICAL AND ANALYTICAL PLANS**

The statistical analysis will be collected in two stages, first at the interim stage (See 10.4.7), and second after the conclusion of all study procedures and database lock.

#### **10.2 STATISTICAL HYPOTHESES**

N/A

#### **10.3 ANALYSIS DATASETS**

The analysis will be performed based on Intention-to-Treat and Per-Protocol in all participants enrolled. Assessment of primary outcomes will be performed on participants who complete at least 75% of applicable time points.

#### **10.4 DESCRIPTION OF STATISTICAL METHODS**

#### 10.4.1 General Approach

Pharmacokinetic parameters will be expressed as a mean, standard deviation and co-efficient of variation for the group total. Similarly, the mean, standard deviation and co-efficient of variation plasma naltrexone and 6-beta-naltrexol will be calculated and tabulated for each time point.

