#### 2.1.1 Metabolism of Naltrexone

NTX is well absorbed orally (96%), but it undergoes a significant first pass metabolism resulting in only 5 to 40% oral bioavailability. Naltrexone is extensively metabolized in humans. Production of the primary metabolite,  $6\beta$ -naltrexol (6-BN), is mediated by dihydrodiol dehydrogenase, a cytosolic family of enzymes. Two other minor metabolites are 2-hydroxy-3-methoxy-6 $\beta$ -naltrexol and 2-hydroxy-3-methoxy-naltrexone. NTX and 6-BN terminal half-life values have been reported as ranging from 2 to 10 hours for naltrexone and 7.5 to 13 hours for 6-BN. Both NTX and 6-BN are excreted primarily by the kidneys. There is a large amount of variation in the metabolism and pharmacokinetics of NTX. In one study, the enzyme kinetics of the formation of 6-BN from NTX using human liver cytosol preparation showed a 2.9 fold variability in Vmax, a 3.2 fold variability in Km and a 7.7 fold variability in intrinsic clearance. The systemic clearance of NTX supersedes the hepatic blood flow, suggesting the NTX is highly extracted and extra hepatic sites of drug metabolism exist.

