# 2.2 STUDY RATIONALE

To date, a number of studies have been carried out on the first generation of the OLANI measuring PK, efficacy and safety data. The current study seeks to collect pilot PK data on the second generation OLANI in healthy participants without a DSM 5 - Substance Related Disorders classification. The use of healthy non-substance dependent volunteers for this protocol greatly reduces the risk of opioid withdrawal related AE's and opioid overdose due to sub-therapeutic naltrexone blood levels being recorded. This pilot data will be used in the planning and design of a large bioequivalence study on the OLANI.

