#### 4.2.4 Secondary Efficacy Endpoints:

- Mean Cmax, Tmax, AUC for naltrexone blood level
- Mean T>MEC for naltrexone, where MEC = 1.33 ng/mL
- Mean Cmax, Tmax, AUC for 6β-naltrexol blood level
- Frequency of AEs and SAEs

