#### 10.4.3 Analysis of the Secondary and Exploratory Endpoint(s)

Pharmacokinetic parameters ( $C_{max}$ ,  $T_{max}$  and  $AUC_{0-\infty}$ , the period of time from insertion that naltrexone plasma concentrations remain above 1.33 ng/mL) will be calculated using a non-compartmental approach. Naltrexone plasma profiles will be plotted graphically for each individual and the study group (concentration-versus-time profile).

Use of opioids, cocaine, marijuana, and alcohol for each day of the study will be determined based on results of urine toxicology and self-report. Proportion of days with substance use for each participant will be summarized.

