#### 10.4.7.2 Efficacy Review

An interim analysis will be carried out once at least 10 participants have completed their Day 180 PK blood time point. Participants, who submitted at least 14 of 19 valid blood samples (including the Day 180 sample) and safety data will be evaluated whether or not they met the MEC criteria (naltrexone blood level above 1.33 ng/mL). The analyzed interim data will be used in the planning and design of a bioequivalence/safety study of the OLANI against a reference extended release naltrexone product.

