#### 10.4.10Tabulation of Individual Response Data

Individual pharmacokinetic and safety data will be tabulated for each time point and included in the appendices of the final study report.

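### Section 10.4.1 plans no geometric or log-scale summary of Cmax and AUC, and no median for Tmax, although the data are meant to help plan a bioequivalence study (minor)

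*Combined protocol and SAP*

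**What the plan says.** Section 10.4.1 sets out how PK results are to be summarised: "Pharmacokinetic parameters will be expressed as a mean, standard deviation and co-efficient of variation for the group total". Plasma concentrations at each time point get the same three statistics. Section 4.2.4 lists "Mean Cmax, Tmax, AUC for naltrexone blood level" as an endpoint, with parallel entries for 6β-naltrexol and for time above the MEC of 1.33 ng/mL. Section 10.4.3 says the parameters "will be calculated using a non-compartmental approach" and mentions no transformation.

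Median and interquartile range appear only for baseline characteristics (10.4.6). Confidence intervals appear only there and for retention (10.4.5). Geometric or log-scale statistics appear nowhere.

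On the use of the data, section 2.2 says: "This pilot data will be used in the planning and design of a large bioequivalence study on the OLANI". Section 10.4.7.2 says of the Day 180 look: "The analyzed interim data will be used in the planning and design of a bioequivalence/safety study". Section 10.4.10 adds: "Individual pharmacokinetic and safety data will be tabulated for each time point and included in the appendices of the final study report".

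**The concern.** Bioequivalence of Cmax and AUC is conventionally tested as a ratio of geometric means, so whoever plans that study needs the variance of the log values. The pilot exists partly to inform that planning, but its summary tables will not show the log-scale variance or any measure of its uncertainty.

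An arithmetic CV can be converted to a log variance by a lognormal formula. In small samples from a skewed distribution the result tends to be too low, because the few large values that carry much of the arithmetic SD are often missing from the sample. The required size of a bioequivalence study rises roughly in proportion to the log variance, so a planner who relied on the tabulated CV would tend to plan too small a study.

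Tmax is a separate matter. From Day 90 the scheduled draws are 30 days apart, against hours or days early on, so Tmax is coarse and unevenly spaced. A mean and SD describe it poorly.

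**Working it through.** **Inputs from the documents.** Section 5.3.1 recruits 20 and expects 50% to complete: 20 × 0.5 = 10, which agrees with the minimum of 10 in section 10.5. The relevant sample sizes are therefore n = 10 and n = 20. The interim also starts from at least 10 participants.

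**Assumptions not in the documents.** Cmax and AUC are lognormal, with log-SD σ between 0.3 and 0.8. Section 2.1.1 describes naltrexone PK as highly variable, but its only relevant number is "a 7.7 fold variability in intrinsic clearance". That is an in-vitro liver-cytosol result with no stated number of preparations, so it does not fix a plasma CV.

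**Formulas.** For lognormal data the population CV is √(exp(σ²) − 1). For σ = 0.3, 0.5 and 0.8 this gives 31%, 53% and 95%. The log variance implied by a sample arithmetic CV is ln(1 + CV²), with CV = SD/mean. The direct estimate is the sample variance of the log values. In large samples the two agree, so the bias is a small-sample effect.

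**Result 1: bias (200,000 simulated samples per row).**

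| n | σ | Mean log variance from arithmetic CV, % of truth | From log values, % of truth | Share of samples below truth: arithmetic / log |
|---|---|---|---|---|
| 10 | 0.3 | 96 | 100 | 61% / 56% |
| 10 | 0.5 | 90 | 100 | 67% / 56% |
| 10 | 0.8 | 76 | 100 | 79% / 56% |
| 20 | 0.3 | 98 | 100 | 58% / 54% |
| 20 | 0.5 | 94 | 100 | 64% / 54% |
| 20 | 0.8 | 84 | 100 | 75% / 54% |

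**Result 2: location.** The arithmetic mean exceeds the geometric mean by a factor exp(σ²/2), that is by 5%, 13% and 38%.

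**Result 3: sampling error.** The 95% limits for a log variance are (n − 1)/χ² times the estimate, using the 97.5% and 2.5% points of χ² on n − 1 degrees of freedom. For n = 10 these are 9/19.02 = 0.47 and 9/2.70 = 3.33. An observed geometric CV of 50% then has limits of about 33% to 105%. For n = 20 the factors are 0.58 and 2.13.

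**Result 4: overall accuracy.** Relative root mean square error of the log variance at n = 10 is 0.48, 0.47 and 0.44 by the arithmetic route, against 0.47 by the log route at each σ. At n = 20 it is 0.35, 0.37 and 0.38 against 0.32.

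**Result 5: upper limits.** A cautious planner may use an upper confidence limit for the variance. At n = 10, a nominal 80% upper limit built on the arithmetic route covers the truth in only 77%, 73% and 61% of samples. Built on the log values it covers 80%.

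**Result 6: what it could mean for the next study.** This is illustrative only: parallel design, limits 0.80 to 1.25, one-sided 5% level, 80% power, true ratio 1.00, pilot n = 10.

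| True CV | n per arm from true CV | From median arithmetic CV | From median geometric CV |
|---|---|---|---|
| 30% | 31 | 27 | 29 |
| 50% | 78 | 64 | 72 |
| 100% | 240 | 162 | 222 |

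**The case against.** The strongest reply is that section 10.4.1 only describes tables. No section makes its CV the planning input or gives a design, margin, power or assumed CV for the later study. Individual PK data will be tabulated (10.4.10) and the sponsor has direct access to source data (section 11), so log-scale SDs can be computed whatever the tables show. If the later study were a crossover, it would need within-subject variance, which one dosing per person cannot supply under any summary. All of this stands.

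It also stands that the bias is small beside the noise at n = 10, where the log route is no more accurate overall; its clear gain in error appears at n = 20. The lognormal assumption matters too. If values were normal with a CV of 30%, the geometric CV at n = 10 would average about 34% and the arithmetic one about 29%.

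Three stronger readings are tempting, and the documents do not support them:

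- **The pilot necessarily passes on an underestimated variability.** The bias is a tendency under an assumed distribution, and the tabulated CV is not the stated planning input. Even the log variance falls below the truth in 56% of samples of 10.
- **Recomputation is impossible before the final report.** Section 10.4.10 places the listings in the final report, but it does not restrict earlier access. The interim in 10.4.7.2 names only MEC status and safety data, not a Cmax or AUC summary.
- **Tmax can take only scheduled times.** Section 7.3.4 records actual sampling times over the first 48 hours, 7.3.5 allows recorded variation, 7.3.8 accepts late samples, and Table 7-1 allows ±10 days at monthly visits. Tmax is coarse but not confined to the schedule.

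What the reply does not answer is that the statistic a bioequivalence planner would ask for first is not among those planned, and adding it costs almost nothing.

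**Conclusion.** The point holds as a minor reporting omission. The plan names no geometric or log-scale summary and no confidence interval for PK parameters, and no median for Tmax, although planning a bioequivalence study is a stated use of the data.

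Under lognormality, converting the tabulated CV would on average understate the log variance by 4%, 10% and 24% with 10 participants, and by 2%, 6% and 16% with 20, at log-SD 0.3, 0.5 and 0.8. These sizes rest on the assumed distribution and spread, on reading the unqualified statistics as arithmetic, and on the tabulated CV being used for planning. No result of this hypothesis-free pilot is invalidated.

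**What to change.** In section 10.4.1:

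- For Cmax and AUC of naltrexone and 6-β-naltrexol, add the geometric mean with its 95% CI, and the geometric CV, computed as √(exp(s²) − 1) from the SD s of the log values, with its 95% CI.
- For Tmax and T>MEC, add the median and range.
- Keep the mean, SD and CV beside them, since normality on either scale is unproven.
- Give the same summaries for any PK parameter reported at the interim, and state in 10.4.7.2 which parameters those are. AUC to infinity will not be mature at Day 180.

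The cost is a few lines of analysis-plan wording and some extra table columns. No new data or visits are needed.

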#### 10.4.2 Analysis of the Primary Endpoint

Participants who submitted at least 75% valid pharmacokinetic blood samples including 2 consecutive monthly naltrexone blood levels recorded at <0.1 ng/mL will be analyzed.

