#### **3 OBJECTIVES AND PURPOSE**

#### **3.1 PRIMARY OBJECTIVES**

To characterize the pharmacokinetic profile ( $C_{max}$ ,  $T_{max}$ , AUC, T>MEC, where MEC = 1.33 ng/mL NTX, Time to  $C_0$  for naltrexone) of the OLANI (2 units).

Primary outcomes used to determine these properties will be based on results from plasma concentration of naltrexone and 6- $\beta$ -naltrexol as ascertained from blood samples taken at the following time points:

- 0, 3, 6, 12, 24, 48 hours
- 4, 8, 14, 21, 28, 35, 42, 49, 56, 90, 120, 150, 180, 210, 240, 270, 300, 330, 360, 390, 420, 450, 480, 510 & 540 days.

Note: 1.33 ng/mL is a target MEC for this protocol. The MEC will be further developed over time.

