#### 4.2 STUDY ENDPOINTS

#### 4.2.1 Primary Endpoint

• The collection of at least 75% pharmacokinetic blood time points including 2 consecutive monthly naltrexone blood levels recorded at <0.1 ng/mL, in 10 participants.

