#### 4.2.2 Secondary Endpoints

- Detailed PK characteristics of the product.
- The collection of safety information and AEs information over 540 days in participants treated with the OLANI.

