### 10.5 SAMPLE SIZE

At the completion of the study it is desirable that a minimum of 10 participants complete a minimum of 75% blood collection time points, including 2 consecutive undetectable values (defined as naltrexone blood levels of <0.1 ng/mL).

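### The analysis set for the PK parameters is stated inconsistently, Time to C0 has no planned analysis, and the 75% rule has no consistent base

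*Combined protocol and SAP*

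**What the plan says.** **Who is analysed**

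- Section 3.1 lists Cmax, Tmax, AUC, T>MEC and Time to C0 in the primary objective and continues: "Primary outcomes used to determine these properties will be based on results from plasma concentration of naltrexone" (and of the metabolite).
- Section 4.2.1 makes the primary endpoint a collection count: "The collection of at least 75% pharmacokinetic blood time points", with two consecutive monthly naltrexone levels below 0.1 ng/mL, in 10 participants. Section 4.2.2 lists "Detailed PK characteristics of the product" as a secondary endpoint.
- Section 10.3 names Intention-to-Treat and Per-Protocol analyses of everyone enrolled, defines neither, and adds: "Assessment of primary outcomes will be performed on participants who complete at least 75% of applicable time points".
- Section 10.4.1: "Pharmacokinetic parameters will be expressed as a mean, standard deviation and co-efficient of variation for the group total".
- Section 10.4.2: "Participants who submitted at least 75% valid pharmacokinetic blood samples including 2 consecutive monthly naltrexone blood levels recorded at <0.1 ng/mL will be analyzed".
- Section 10.4.3 says that Cmax, Tmax, AUC to infinity and the time above 1.33 ng/mL "will be calculated using a non-compartmental approach". It names no set and does not list Time to C0.
- Section 10.5: "it is desirable that a minimum of 10 participants complete a minimum of 75% blood collection time points", with two consecutive undetectable values.

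**What feeds the 75%**

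Section 7.2.3 has participants leave after two consecutive monthly levels below 0.1 ng/mL and budgets 32 naltrexone samples to Day 540. Table 7-1 marks a PK draw at the Final Visit. Section 7.3.5 allows PK draws to be missed when visits are remote. Section 5.3.1 expects 10 of 20 participants to complete.

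**The concern.** An analyst cannot tell from the plan who enters the table of mean PK parameters. The candidates are everyone enrolled (10.3, first sentence), those with 75% of applicable points (10.3, second sentence), those who also reached two levels below 0.1 ng/mL (10.4.2), or the undefined group total (10.4.1).

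The choice matters in two ways. Requiring two levels below 0.1 ng/mL conditions Time to C0 on having been observed, so the analysis of a duration is restricted by that duration. It also removes from the Cmax and Tmax summaries people who left later but had already given the samples those parameters need.

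The base of the 75% raises a separate problem: it decides who counts toward the 10 participants of the primary endpoint. The trial is open label, levels come back during follow-up because they trigger exit, and there is a Day 180 interim look. A set or base left open could therefore be settled with the data in view. The results are meant to guide the design of the next study.

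**Working it through.** **1. The plan's own figures.** With 50% completing, 10/(1 - 0.5) = 20 recruits, as in Section 5.3.1. The schedule in Section 3.1 has 6 points from 0 to 48 hours, 9 from Day 4 to Day 56 and 16 monthly from Day 90: 6 + 9 + 16 = 31. To Day 180 it is 6 + 9 + 4 = 19, matching the interim rule in Section 10.4.7.2.

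**2. The base of the 75%.** Section 10.3 says applicable, without definition. Sections 4.2.1, 10.4.2 and 10.5 give no base. The schedule lists 31 points and Section 7.2.3 budgets 32 samples; the extra one is plausibly the Final Visit draw, which is an inference. The threshold is 0.75 x 31 = 23.25, so 24, or 0.75 x 32 = 24. By Day 300 a full attender has given 6 + 9 + 8 = 23 scheduled samples. If the second level below 0.1 ng/mL is the Day 300 sample:

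| Base | Score | Meets 75% |
|---|---|---|
| Points due up to exit | 23/23 = 100% | yes |
| 32, Final Visit draw counted | 24/32 = 75.0% | yes |
| 31, Final Visit draw not counted | 23/31 = 74.2% | no |

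Missed draws widen the gap. With exit at Day 360 (25 points), 19 are needed on the applicable base, so 6 may be missed; on a base of 31, 24 are needed and only 1 may be missed.

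**3. Precision for Cmax and Tmax.** Assume constant dropout unrelated to PK, with half still present at exit. The number followed at Day 180 is 20 x 0.5^(180/exit day): exit at Day 360 gives 20 x 0.707 = 14.1, and exit at Day 480 gives 20 x 0.771 = 15.4. Simulation over the scenarios in step 4 gives 14.0 to 15.4, so a completer set of 10 drops about 4 to 5 usable participants. The 95% CI half-width is t(0.975, n-1)/sqrt(n) in SD units: 2.262/3.162 = 0.715 at n=10 and 2.160/3.742 = 0.577 at n=14. The ratio is 0.577/0.715 = 0.81, so about 19% narrower.

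**4. Bias in mean Time to C0.** The documents give no distribution. Assumed: lognormal with median 300 to 420 days and log-SD 0.15 to 0.35; monthly sampling; exit at the second level below 0.1 ng/mL; exponential dropout unrelated to PK, tuned so that half of 20 reach that sample; no missed draws; follow-up past Day 540 where needed (Section 7.3.9); 400,000 simulated participants per scenario. The main cases have at most 2% past Day 540, in line with Section 4.1.

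| Median (days) / log-SD | Past Day 540 | Bias, applicable base | Of 20 meeting the 10.4.2 rule: applicable / 32 with Final Visit / 31 |
|---|---|---|---|
| 300 / 0.15 | 0% | -1.3% | 10 / 9.2 / 7.3 |
| 300 / 0.25 | 1.7% | -3.6% | 10 / 7.8 / 6.1 |
| 360 / 0.15 | 1.0% | -1.4% | 10 / 10.0 / 9.7 |

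The bias is negative because slower participants have longer in which to drop out. In the main cases it is 4 to 12 days, below the 30-day sampling interval. Over all nine scenarios it runs from -1.3% to -7.3%. If visits stopped at Day 540, the main cases would give -1.4% to -4.3%.

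**5. Check of the remedy.** In 4,000 simulated trials of 20 per scenario, the completers' median was off by -1.1% to -6.1% without a Day 540 cap, and by up to -14.6% with one. With and without the cap, a Kaplan-Meier median was off by -0.2% to +4.1% when dated at the first level below 0.1 ng/mL, and by -1.0% to +1.4% when dated at the confirming sample and then shifted back.

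**The case against.** Section 10.4.2 is headed for the primary endpoint, which is a collection count, so it need not govern the PK parameters at all. Section 10.4.3 plots every individual and Section 10.4.10 tabulates every individual's PK data, so nothing is hidden. The study is a descriptive pilot with no hypotheses, and Section 10.5 calls 10 completers only desirable. This stands in part: the harm arises only if the completer set is used for the PK summaries. But Section 10.4.3 then has no set of its own, and the means, SDs and CVs that are the study's product depend on who is averaged.

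A reader might also infer that the rule means 75% of all 31 points, so that full attenders whose levels fall early are excluded and durations are overstated. On that worst-case reading the error in mean Time to C0 would be +5.0%, +10.2% and -0.4% in the main cases (-1.7% to +14.4% over all nine). The documents do not support it. No section states a base of 31. Section 10.3 says applicable, Section 7.2.3 treats later monthly points as not needed, and the interim rule uses 14 of 19, the points due by then. Counting the Final Visit draw against the 32-sample budget also lets the Day 300 case qualify, and the errors become +0.8%, +4.5% and -1.3%. What stands is that the base is unstated where the endpoint is defined and analysed.

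**Conclusion.** The point holds as an inconsistency that is cheap to remove. Without any assumption: Sections 10.3 and 10.4.2 give different sets, Section 10.4.3 gives none, Time to C0 is in the primary objective but not in the listed analyses, Per-Protocol is undefined, and the base of the 75% is not the same throughout.

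The size rests on assumed dropout and an assumed distribution of Time to C0. Using completers costs about 4 to 5 participants for Cmax and Tmax. The bias in mean Time to C0 on the applicable base is small, about -1% to -4% in the main cases and up to -7% with wide variability. The larger practical risk is that the count toward the 10 participants of the primary endpoint can turn on the base. The change should be made, at low priority within that class; it does not undermine the trial.

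**What to change.** - **Set.** In Sections 10.3 and 10.4.3, compute each PK parameter in all implanted participants with adequate samples for that parameter. For Cmax and Tmax, adequacy should include a minimum length of follow-up as well as a share of points, so that someone who leaves in the first days does not qualify on a local peak. Keep the Section 10.4.2 rule for the collection endpoint and for a completer sensitivity analysis.
- **Time to C0.** Add it to Section 10.4.3 as the first of two consecutive monthly levels below 0.1 ng/mL. Beside the planned means, report a Kaplan-Meier or interval-censored summary of Time to C0 and T>MEC in all implanted participants. State the assumption that dropout is unrelated to PK, and how implant removal or expulsion is handled in the analysis. If Kaplan-Meier is used for Time to C0, date the event at the confirming sample and then report the first.
- **Denominator.** Use one base in Sections 4.2.1, 10.3, 10.4.2 and 10.5: time points scheduled up to the participant's own study exit. Say whether the Final Visit draw and draws missed at remote visits count.
- **Per-Protocol.** Define it or delete it.

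The cost is wording and modest programming, with no new visits or samples. The downside is medians with wide intervals at n=20. In the simulations the median was always reached with follow-up past Day 540; with a cap it was not reached in up to 8% of trials (median 420 days, log-SD 0.35).
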